5 EFFICACY AND SAFETY ENDPOINTS

Data for the efficacy endpoints will be recorded on an e-diary. This e-diary consists of a:

- 5-day Weekday Diary (bladder diary, Monday Friday), which is used for a 5-day period to record micturition frequency and incontinence episodes, and
- 2-day Weekend Episodic Diary (Saturday and Sunday), which is used to record micturition frequency, incontinence episodes, (pee) volume measurements, and worst leakage severity.

A valid diary day for:

• "Volumes"

In the 2-day Weekend Episodic Diary, is any e-diary day for which at least one "Pee Volume" greater than 0 mL is recorded with complete date and time.

- "Micturitions"
- In 2-day Weekend Episodic Diary, is any diary day for which at least once "Pee Volume" greater than 0 is recorded.
- In 5-day Week Diary, is any diary day for which the response to the question "Number of times using the toilet during the day/night" is not missing.
 - "Incontinence episodes"
- In 2-day Weekend Episodic Diary, is any diary day for which at least:
 - One micturition ("Pee Volume" >0) and
 - One "Leakage" or "Pee in toilet and Leakage" are recorded.
- In 5-day Week Diary, is any diary day for which:
 - The response to the question "How was your day/night" is not missing.

A valid diary for an analysis visit is a diary with at least 4 valid diary days within that analysis visit window. If for more than 7 days the diary is filled in prior to a visit, only the last 7 days prior to that visit will be used for calculation of the efficacy endpoints.

The number of valid diary days: Count of the valid diary days during the 7-day diary period. Days of visits to the clinic will not be counted as valid diary days.

In the event that in the 2-day Weekend Episodic Diary there are two entries with the same collection date and time but with different times of entry on the device, the last entry (time) will be used for analysis.

For several of the secondary efficacy endpoints, diary data will be classified as either "daytime" or "nighttime", where "daytime" is considered to mean "between waking up in the morning and going to sleep later the same day or next day" and "nighttime" means "between going to sleep on a day and waking up on the same or next day".

Whether an entry into the 5-day Week Diary is done during daytime or nighttime is captured on this diary.

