For entries into the 2-day Weekend Episodic Diary, "daytime" and "nighttime" will be derived from the time the subject went to sleep and the time the subject awakened. These times are entered on this diary by the subject.

The go-to-bed time for Sunday is not captured in the diary. In order to distinguish between daytime and nighttime on Sunday the go-to-sleep time will be imputed as occurring a short time after the second (evening) SBPM was performed: time of second SBPM plus 1 hour. If there is no time entered in the diary for the evening SBPM, then the go-to-sleep time will be imputed as 23:59 (on Sunday).

5.1 **Primary Efficacy Endpoint**

The primary efficacy endpoint is the change from baseline to week 12/EoT in mean number of micturitions per 24 hours in children (5 to <12 years of age).

Number of micturitions per 24 hours is calculated from:

• The response to the questions "Number of times using the toilet during the night" and "Number of times using the toilet during the day" on the 5-day Week Diary,

and

• The number of times a "Pee in toilet" or a "Pee in toilet and leakage" was entered into the 2-day Weekend Episodic Diary.

For a weekend day:

- The daytime micturitions will be derived from the number of times a "Pee in Toilet" or a "Pee in Toilet and Leakage" was entered into the 2-day Weekend Episodic Diary between the time the subject woke up (exclusive) and went to sleep (inclusive).
- The nighttime micturitions will be derived from the number of times a "Pee in Toilet" or a "Pee in Toilet and Leakage" was entered into the 2-day Weekend Episodic Diary between the time the subject went to sleep (exclusive) and woke up (inclusive).

The total number of micturitions per weekend day is equal to the total number of times, in the diary, an amount of pee was recorded during daytime and nighttime for that day.

For each subject, the mean number of micturitions at Visit x (x=4, 5, 6, 7), using all available (non-missing) number of micturitions per 24 hours for the valid days in the diary (at least 4 and maximally 7), will be calculated as:

Sum of the number of micturitions (per 24 hours) over the valid diary days prior to Visit x Number of valid diary days

Note:

- If for a week day (Monday Friday):
 - the number of daytime micturitions is missing but the number of nighttime micturitions is not missing then the number of micturitions for that day is considered to be the number of micturitions during the nighttime.

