- the number of nighttime micturitions is missing but the number of daytime micturitions is not missing then the number of micturitions for that day is considered to be the number of micturitions during the daytime.
- both daytime and nighttime micturitions are missing then the number of micturitions for that day is considered missing.
 - If for a weekend day (Saturday Sunday):
- No pee volume is recorded for Saturday or for Sunday then the number of micturitions is missing for Saturday or Sunday, respectively.
- No pee volume is recorded for Saturday and for Sunday then the number of micturitions is missing for both days.

If the wake-up time is the same as the time of micturition, then the micturition will be counted as a nighttime micturition.

Note: the first micturition occurring at or after the time of wake-up is considered a nighttime micturition.

A micturition episode is counted as micturition regardless of whether volume voided was recorded or not.

A micturition will also be counted if the subject assessed an episode as both micturition and incontinence (leakage).

If data of more than 7 days prior to a visit is available, only the last 7 days prior to the visit will be used for the analysis.

The baseline will be defined by the micturitions results obtained from the diary 7 days prior to visit 3/week 0 (baseline).

The visit 7/week 12/EoT visit will be defined as the subject's value at week 12 or in case of missing week 12 data, the last available result post-baseline.

Subjects without baseline or any post-baseline value will not be included in the change from baseline calculation although they will be included in the summary for either baseline or any post-baseline visit whichever timepoint the data is available.

Change from baseline to visit 7/week 12/EoT is defined as:

Result at visit 7/week 12/EoT – Result at baseline (visit 3/week 0).

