6.10 Additional Conventions

6.10.1 Analysis Windows

The study protocol gives the overall study schedule and the permissible intervals for these visits expressed as the number of days relative to visit 3/baseline. The total time each subject will be in the study will not exceed 18 weeks with a maximum of a screening period of 4 weeks and a maximum of 14 weeks for the investigational period.

Analyses will not exclude subject data due to the subject's failure to comply with the visit schedule.

Visit Windows for Efficacy and Safety Parameters

CRF visit	Target day relative to Baseline (Visit 3, Day -1)	Analysis Window	Analysis visit
Bladder e-d	liary		
Visit 3	Last value prior to first dose	Day -7 to Day 1 (prior to first dose)	Baseline
Visit 4	Day 14	Day 7 to Day 21	Week 2
Visit 5	Day 28	Day 22 to Day 42	Week 4
Visit 6	Day 56	Day 43 to Day 70	Week 8
Visit 7	Day 84	Day 71 to Day 91	Week 12
ЕоТ	Day 84	Day 1 to \leq Last dose of double- blind study drug	ЕоТ
Acceptabili	ty questionnaires		
Visit 7	Day 84	Day 71 to Day 91	Week 12
ЕоТ	Day 84	Day 1 to \leq Last dose of double- blind study drug	ЕоТ
SBPM			
Visit 3	Last value prior to first dose	Day -7 to Day 1 (prior to first dose)	Baseline
Visit 4	Day 14	Day 7 to Day 21	Week 2
Visit 5	Day 28	Day 22 to Day 42	Week 4
Visit 6	Day 56	Day 43 to Day 70	Week 8
Visit 7	Day 84	Day 71 to Day 91	Week 12
ЕоТ	Day 84	Day 1 to \leq Last dose of double- blind study drug	ЕоТ
Table contin	nued on next page		

All the assessments will be allocated to CRF visit based on Table 10.

CRF visit	Target day relative to Baseline (Visit 3, Day -1)	Analysis Window	Analysis visit	
Vital signs				
Visit 1			Screening	
Visit 3	Last value prior to first dose	Day -7 to Day 1 (prior to first dose)	Baseline	
Visit 5	Day 28	Day 22 to Day 56	Week 4	
Visit 7	Day 84	Day 57 to Day 91	Week 12	
ЕоТ	Day 84	Day 1 to \leq Last dose of double- blind study drug	ЕоТ	
Visit 8 [#]	Day 98	Day 92 or EoT + 1 to no more than 17 days after EoT	Week 14 (EoS)	
ECG	-			
Visit 1			Screening	
Visit 3	Last value prior to first dose	Day -7 to Day 1 (prior to first dose)	Baseline	
Visit 5	Day 28	Day 22 to Day 56	Week 4	
Visit 7	Day 84	Day 57 to Day 91	Week 12	
ЕоТ	Day 84	Day 1 to \leq Last dose of double- blind study drug	ЕоТ	
Clinical Lab	ooratory Tests (Hematology, B	iochemistry and Urinalysis)		
Visit 1			Screening	
Visit 3	Last value prior to first dose	Day -7 to Day 1 (prior to first dose)	Baseline	
Visit 5	Day 28	Day 22 to Day 56	Week 4	

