Visit 7	Day 84	Day 57 to Day 91	Week 12	
ЕоТ	Day 84	Day 1 to \leq Last dose of double- blind study drug	ЕоТ	
Visit 8 [#]	Day 98	Day 92 or EoT to no more than 17 days after EoT	Week 14 (EoS)	
Post Void Residual (PVR) Volume				
Visit 3	Last value prior to first dose	Day -7 to Day 1 (prior to first dose)	Baseline	
Visit 5	Day 28	Day 22 to Day 56	Week 4	
Visit 7	Day 84	Day 57 to Day 91	Week 12	
ЕоТ	Day 84	Day 1 to \leq Last dose of double- blind study drug	ЕоТ	
Visit 8 [#]	Day 98	Day 92 or EoT to no more than 17 days after EoT	Week 14 (EoS)	

[#]Visit 8 may occur earlier due to early discontinuation as it is the last scheduled study visit.

For non-diary data, if a subject has more than one non-missing value within a visit window, the non-missing assessment which is closest to the target day within a window will be used. If two or more values are equally close and on different days, the latest non-missing value will be used. If two or more values are equally close and on the same day, the mean will be used for continuous variables or the worst observed case for categorical variables.

For diary data, the assessment date for the whole diary will be considered to be the date of the last valid day of the diary. If more than one diary has an assessment date within the same window, and if this results in more than one non-missing value of a diary variable, the non-missing value with the diary assessment day that is closest to the target day will be used. In case of ties on different days, the later non-missing value will be used. In case of ties located on the same side of the target day (i.e., more than one value for the same day), the mean of the values will be used for continuous variables and the worst value for categorical variables. For analyzing diary data the labels of the study visits will not be used, they will be assigned based on the dates of assessment.

A two-day window around the visit date will be applied for the assignment of study period for exposure data.

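### The SAP's 4-valid-day diary rule, counted inside the Table 10 windows, conflicts with its whole-diary allocation and its baseline definition, and read literally rejects a complete week-4 diary when visit 5 is on Day 25

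*SAP*

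**What the plan says.** SAP 5 gives the validity rule: "A valid diary for an analysis visit is a diary with at least 4 valid diary days within that analysis visit window". It also excludes clinic days ("Days of visits to the clinic will not be counted as valid diary days") and, for an over-long diary, says that "only the last 7 days prior to that visit will be used for calculation of the efficacy endpoints". Its next definition counts valid days over the seven-day diary period and does not mention a window.

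SAP 5.1 averages micturitions "for the valid days in the diary (at least 4 and maximally 7"). On baseline it says: "The baseline will be defined by the micturitions results obtained from the diary 7 days prior to visit 3/week 0 (baseline"). SAP 5.2 uses the same seven days for the secondary endpoints.

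Table 10 in SAP 6.10.1 sets the baseline diary window as "Day -7 to Day 1 (prior to first dose") and the week-4 window as "Day 22 to Day 42". Below the table, the same section treats the diary as one unit: "the assessment date for the whole diary will be considered to be the date of the last valid day of the diary". It adds that visit labels are not used for diary data and that dates decide.

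Protocol Table 1 puts visit 3 on Day -1, with dosing from Day 1, the day after. Visits 4, 5, 6 and 7 are on Days 14, 28, 56 and 84, each ± 3 days. Protocol 7.1.1 has each 7-day diary start about 7 days before the visit.

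**The concern.** Two rules decide whether a diary counts for an analysis visit. One tests individual days against the window; the other places the whole diary by a single date. For some permitted visit dates they disagree, and the SAP does not say which prevails. Two programmers could both follow the SAP and build different datasets.

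Baseline has a second mismatch: the window does not contain all seven days that SAP 5.1 and 5.2 name. Baseline is both subtracted in the change score and used as the covariate in the primary ANCOVA, and SAP 5.1 leaves a child without a baseline out of the change calculation. Inclusion criterion 15 also uses the 7 days before visit 3 and states no minimum number of completed days. A child could therefore be randomised on diary data that the SAP later rejects.

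**Working it through.** The plan gives no figure of its own to reproduce here; the check is day counting.

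**Inputs.** Windows for baseline, week 2, week 4, week 8 and week 12: Days -7 to 1 (pre-dose), 7–21, 22–42, 43–70 and 71–91 (SAP Table 10). Visit days and allowances: protocol Table 1. Threshold: 4 valid days (SAP 5). There is no Day 0. I assume that the diary is the 7 calendar days ending the day before the visit and that all 7 are completed.

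**Formula.** For a visit on Day v the diary covers Days v−7 to v−1. With a window from L to U,

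days in window = min(U, v−1) − max(L, v−7) + 1.

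**Baseline.** Visit 3 is Day -1, so the diary is Days -8 to -2. With L = -7: −2 − (−7) + 1 = 6 of 7. Day -8 is outside. A child with exactly 4 valid days, one of them Day -8, has 4 − 1 = 3 in the window and fails.

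**Week 4 (L = 22).**

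| Visit 5 on | Diary days | In window | 4-day rule (SAP 5) | Last day in window (SAP 6.10.1) |
|---|---|---|---|---|
| Day 25 | 18–24 | 24 − 22 + 1 = 3 | fails | yes |
| Day 26 | 19–25 | 4 | passes, no margin | yes |
| Day 27 | 20–26 | 5 | passes | yes |
| Day 28 | 21–27 | 6 | passes | yes |
| Days 29–31 | from 22–28 to 24–30 | 7 | passes | yes |

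At Day 25 the other four days (18–21) lie in the week-2 window, but the diary is dated Day 24, so it does not become a week-2 diary either.

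**Week 2 (L = 7).** Visit 4 on Day 11: diary Days 4–10, so 10 − 7 + 1 = 4, with no margin. Days 12 and 13 give 5 and 6; Days 14–17 give 7.

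**Weeks 8 and 12.** The earliest and latest permitted diaries are Days 46–52 and 52–58 (window 43–70), and Days 74–80 and 80–86 (window 71–91). All 7 days are inside at every permitted date.

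**Under whole-diary allocation.** The baseline diary is dated Day -2 and the Day-25 diary Day 24. Both fall in their windows with 7 of 7 days, and no complete diary at a permitted date is lost at any visit.

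**The case against.** The strongest reply is that SAP 6.10.1 already settles the matter: the diary is placed as a unit, and SAP 5.1 and 5.2 supply the seven-day baseline. That is a sensible reading and probably the intended one. But the sentence in SAP 5 expressly ties the count to the window, and nothing gives the other rule precedence.

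Three stronger readings are tempting, and the documents do not support them.

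- A reader might infer that every on-schedule child loses a baseline day from the mean. The sentence in SAP 5 is a threshold. It does not remove out-of-window days from the average, SAP 5.1 averages up to 7 valid days, and 6 in-window days pass the test.
- A reader might infer that the LOCF source is lost for an early dropout. Table 10 has a separate EoT row running from Day 1 to the last dose, and all of Days 18–24 lie inside it for a child dosed through Day 24. SAP 5.1 falls back on the last available post-baseline result, so that diary can still supply the value.
- A reader might infer that a late first dose, for example through courier dispensing under protocol Table 12, pushes baseline days out of the window. Table 10 and the protocol tie Day 1 to visit 3, so a late dose does not move the diary days.

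It is also fair to say that only 1 of the 7 permitted visit-5 days fails outright.

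**Conclusion.** The conflict stands and should be corrected, but its reach is limited. On the literal wording of SAP 5, the clear loss is the week-4 value for children whose visit 5 falls on Day 25. It also reaches children with visit 5 on Day 26 who miss one of Days 22–25, and the week-2 value for those with visit 4 on Day 11 who miss one of Days 7–10. These losses affect the by-visit summaries, the repeated-measures model (SAP 6.4.1.3.3) and the multiple-imputation analyses (SAP 6.4.1.3.5), where a collected value would be treated as missing.

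The direct route into the primary analysis is the rare child with exactly 4 valid baseline days that include Day -8. A complete week-12 diary is never affected.

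The documents do not say how visit dates or diary completion are distributed, so the number of children cannot be estimated. The counts assume that diaries end the day before the visit; the protocol's start time is only approximate.

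**What to change.** Three wording changes:

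1. In SAP 5, remove the tie to the analysis window and require at least 4 valid days among the 7 days before the visit.
2. State there that the whole diary is then allocated to an analysis visit by its last valid day, as SAP 6.10.1 already provides, so that the windows apply to diaries and not to single days.
3. In Table 10, set the baseline diary window to the 7 days before visit 3 (Day -8 to Day -2), matching SAP 5.1 and 5.2.

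One pattern would remain to be decided: with visit 5 on Day 25, a child who completes only Days 18–21 has a last valid day of Day 21 and would be dated into week 2. A sentence can settle it.

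The cost is SAP text and one programming rule. No new data are needed, and SAP 1 allows revisions before hard lock.

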5.2.3 Mean Number of Daytime Incontinence Episodes per 24 hours

For a week day the number of Incontinence Episodes per 24 hours will be derived from "Number of Leakages During the Day" and "Number of Leakages During the Night" of the 5-day Week Diary. Incontinence episodes on measuring days will be classified as daytime or nighttime episodes as entered in the 5-day Week Diary.

For a weekend day the number of incontinence episodes will be derived from the times a "Leakage" or a "Pee in Toilet and Leakage" was entered into the 2-day Weekend Episodic Diary. Whether an Incontinence Episode was during daytime or nighttime will be based on the time-points the subject went to sleep and woke-up.

For each subject, the mean number of incontinence episodes per day/night (during the day/night) at Visit x (x=4, 5, 6, and 7) will be calculated using all available (non-missing) number of incontinence episodes for the valid diary days in the 5-day Week Diary and in the 2-day Weekend Episodic Diary for daytime in the 7-day period before the visit:

Mean No. of Daytime Incontinence Episodes at Visit x =

Total number of "Daytime Leakage Counts" over the Valid Diary Days prior to Visit x Number of Valid Diary Days

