5.4.2.2 Self-Measurement of Vital Signs

Self-blood pressure monitoring (SBPM; SBP and DBP) will be measured at visit 2/week 2, visit 3/baseline, visit 4/week 2, visit 5/week 4, visit 6/week 8, and visit 7/week 12 (EoT) and whenever deemed necessary by the investigator.

SBPM will be measured once in the morning and evening during the 2-day Weekend Episodic Diary collection period. Measurements will be taken in the sitting position (when possible, otherwise supine, but always in the same position). Preferably, the right arm should be used. Morning measurement should be taken before IP intake and evening measurement should be taken prior to bedtime.

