6.10.2.1 Imputation Rules for Diary Dates

The go-to-bed time for Sunday is not captured in the diary. This time will be imputed as occurring a short time after the second (evening) SBPM was performed: time of second SBPM plus 1 hour. If there is no time entered in the diary for the evening SBPM, then the go-to-sleep time will be imputed as 23:59 (on Sunday), see Section 5.

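### The 23:59 fallback for a missing Sunday bedtime counts some events during sleep as daytime in two secondary endpoints

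*SAP*

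**What the plan says.** SAP 5 defines daytime as running from waking until going to sleep, and nighttime as the rest. For the weekend diary it says that the two "will be derived from the time the subject went to sleep and the time the subject awakened. These times are entered on this diary". One time is missing by design: "The go-to-bed time for Sunday is not captured in the diary" (SAP 6.10.2.1, also stated in SAP 5).

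The first-choice substitute is "time of second SBPM plus 1 hour". This follows the child to some extent, because SAP 5.4.2.2 says that the "evening measurement should be taken prior to bedtime". The second-line substitute does not: "If there is no time entered in the diary for the evening SBPM, then the go-to-sleep time will be imputed as 23:59 (on Sunday". SAP 6.10.2.1 repeats it: "then the go-to-sleep time will be imputed as 23:59 (on Sunday), see Section 5".

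The imputed time is then used directly. SAP 5.2.3 on incontinence says: "Whether an Incontinence Episode was during daytime or nighttime will be based on the time-points the subject went to sleep and woke-up". SAP 5.2.4 counts weekend daytime micturitions between waking and sleep, and SAP 5.3.1 uses the same boundary for the responder classification.

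**The concern.** The efficacy population is children aged 5 to under 12, many of whom would be expected to be asleep well before midnight on a Sunday. With the cut-off fixed at 23:59, a leak or void after sleep onset but before that time is labelled daytime, contrary to the SAP's definition. Daytime incontinence is meant to separate daytime leakage from bed-wetting, so this error works against its purpose.

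Whether a child is affected depends on whether a blood pressure time was entered that evening, which has nothing to do with bladder function and can vary from visit to visit. A Sunday without an SBPM time still counts, because diary-day validity in SAP 5 does not depend on SBPM. None of the sensitivity analyses in SAP 6.4.1.3, which SAP 6.4.2 extends to the secondary endpoints, varies the bedtime rule.

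**Working it through.** The plan states no figure that depends on this rule, so there is nothing to reproduce. The steps below apply the SAP's derivations directly.

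**Inputs from the documents.** Fallback time 23:59 (SAP 5, 6.10.2.1). Valid diary days in a visit mean: 4 to 7 (SAP 5, 5.1). Entry minimum of 1 daytime leak per day on average (Protocol 5.1, criterion 16). Responder formula (SAP 5.3.1).

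**Assumptions, not in the documents.** Sleep onset between 19:30 and 22:00. An event occurs in the window and is recorded with its true time. The shares of diaries without an SBPM time are also assumed.

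1. *Length of the window.* 23:59 minus 19:30 is about 4.5 h; 23:59 minus 22:00 is about 2.0 h.

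2. *Shift in one child's visit mean.* Each misplaced event adds 1/(valid diary days):
   - 7 days: 1/7 = 0.14
   - 6 days: 1/6 = 0.17
   - 5 days: 1/5 = 0.20
   - 4 days: 1/4 = 0.25

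   Against the entry minimum of 1 per day, one event is 14% to 25%. That is the least favourable benchmark; a child with more leaks has a smaller relative shift.

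3. *Responder classification.* R = (visit count − baseline count) / baseline count × 100%. Take 7 daytime leaks at baseline.
   - True week-12 count 0: R = −100%, complete responder. With one misplaced leak: (1 − 7)/7 = −85.7%, partial responder.
   - True count 3: (3 − 7)/7 = −57.1%, partial responder. With one misplaced leak: (4 − 7)/7 = −42.9%, non-responder.

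4. *Primary endpoint.* The weekend 24-hour total adds day and night (SAP 5.1). If the true Sunday split is 8 day + 2 night = 10, the imputed split is 9 + 1 = 10. Nothing changes.

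5. *Dry days.* Under SAP 5.2.5 a weekend leak at any hour makes the day wet, so this endpoint does not change either.

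6. *Average effect on change from baseline.* Approximate bias = (share without SBPM time at week 12 − share at baseline) × events in the window / valid days.
   - 10-point gap and 0.5 events: 0.10 × 0.5/7 = 0.007 to 0.10 × 0.5/4 = 0.013 per day.
   - 30-point gap and 1 event: 0.30 × 1/7 = 0.043 to 0.30 × 1/4 = 0.075 per day.
   - No gap and equal event rates at both visits: zero.

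   The treatment difference is biased only if this quantity differs between arms.

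**The case against.** The rule is a second-line fallback. SBPM is required every morning and evening of the weekend diary and is entered in the same device, and Protocol 7.6 has sites check completion before each visit and retrain where needed. The 23:59 value applies only when that fails on one particular evening. It is a transparent end-of-day convention, prespecified, stated identically in two places and applied to both arms of a double-blind trial. The documents give no bedtimes and do not say how a leak during sleep is timed; one logged on discovery the next morning falls after 23:59 and stays nighttime. All of this stands, and it limits the point to a refinement.

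A reader might infer more than the documents support:
- That everything after the child falls asleep becomes daytime. Only events timed up to 23:59 do.
- That the primary endpoint is distorted. It sums day and night.
- That 0.14 to 0.25 per day is the effect on the endpoint. It is the effect of one event in one affected child.
- That the treatment comparison is biased. This needs missing SBPM times, or events in the window, to differ by arm, and nothing in the documents suggests that they do.

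What the objection does not remove is the mismatch between the fallback and the SAP's own definition, given that a time specific to the child appears to be available.

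**Conclusion.** The point holds as a minor one. When the Sunday evening SBPM time is absent, the fallback misclassifies any event timed between actual sleep onset and 23:59. This reaches only the Sunday contribution to daytime incontinence, daytime micturitions and the exploratory responder classification; the primary endpoint and dry days are untouched.

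One event shifts one child's visit mean by 0.14 to 0.25 per day and can move a child across a responder boundary. The average effect is probably small added noise, with bias in change from baseline only if SBPM completion or the number of events in the window differs between baseline and week 12. These sizes rest on assumed bedtimes and event times, and the frequency of missing SBPM times is not given.

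That the Saturday bedtime is recorded is an inference: SAP 5 says sleep times are entered on the weekend diary and names only Sunday's as not captured. No sentence states it outright.

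**What to change.** In SAP 5 and 6.10.2.1, replace the fallback as follows: when the Sunday evening SBPM time is missing, use the subject's Saturday go-to-sleep clock time from the same weekend diary; use 23:59 only if that is missing as well. First confirm from the diary specification that the Saturday time is collected.

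The cost is one sentence in two sections and a small programming change. No new data are needed, it can be done blinded, and SAP 1 allows revisions before database hard lock. The downside is that Saturday bedtime may be later than Sunday's, so misclassification is reduced, not removed.

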5.2.4 Mean Number of Daytime Micturitions per 24 hours

For a week day the daytime micturitions will be derived from "Number of Times using the Toilet During the Day" was entered into the 5-day Week Diary.

For a weekend day the daytime micturitions will be derived from the number of times a "Pee in Toilet" or a "Pee in Toilet and Leakage" was entered into the 2-day Weekend Episodic Diary between the time the subject woke-up (exclusive) and went to sleep (inclusive). However, the first micturition occurring at or after the time of wake-up it is considered a nighttime micturition, see Section 5.1.

The total number of micturitions per weekend day is equal to the total number of times, in the diary, an amount of pee was recorded during daytime for that day.

For each subject, the mean number of daytime micturitions at Visit x (x=4, 5, 6, and 7) in the week before the visit will be calculated as:

Sum of the Number of Daytime Micturitions (per day) over the Valid Diary Days prior to Visit x Number of Valid Diary Days

5.2.5 Number of Dry (incontinence free) Days per 7 Days at the End of the 12-weeks Treatment Period

For a week day a "Dry (incontinence free) Day" is defined as a day where the response is "Dry" to the question "How was your Day" and to "How was your Night".

Let D_{dry} be the number of valid diary days where the response to both questions was "Dry". Let D_{wet} be the number of valid diary days where the response to one of the two questions or to both questions was "Wet".

For a weekend day a "Dry (incontinence free) Day" is defined as a day where no "Leakage" and no "Pee in toilet and leakage" are reported. A "Wet (incontinence) Day" is defined as a day where a "Leakage" or a "Pee in toilet and leakage" is reported.

If $(D_{dry} + D_{wet}) > 3$, then the number of dry days per 7 days at Visit 7 will be calculated for a subject as:

 $\frac{D_{dry}}{(D_{dry}+D_{wet})} \times 7$, otherwise its value is missing.

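### SAP 5.1 and 5.2.4 each contain a sentence that totals weekend micturitions by recorded volumes, which contradicts the toilet-entry count in the same sections and undercounts on partly measured days

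*SAP*

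**What the plan says.** SAP 5.1 (Primary Efficacy Endpoint) names the source of the weekend count as "The number of times a 'Pee in toilet' or a 'Pee in toilet and leakage' was entered into the 2-day Weekend Episodic Diary". It then defines weekend daytime and nighttime micturitions from the same two entry types, split by sleep and wake times.

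The next sentence gives a different total, taken over day and night together: "The total number of micturitions per weekend day is equal to the total number of times, in the diary, an amount of pee was recorded".

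The notes later in 5.1 return to the first rule: "A micturition episode is counted as micturition regardless of whether volume voided was recorded or not".

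SAP 5.2.4 (daytime micturitions, a secondary endpoint) has the same structure. It starts from toilet entries between waking and sleeping, then sets the weekend total "equal to the total number of times, in the diary, an amount of pee was recorded during daytime for that day". It does not repeat the statement that volume is irrelevant.

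Two other rules determine when this matters. Under SAP 5, a weekend day is valid for micturitions if it "is any diary day for which at least once 'Pee Volume' greater than 0 is recorded". Under 5.1, a weekend day with no volume at all has a missing count, and the visit mean is taken "for the valid days in the diary (at least 4 and maximally 7), will be calculated as" the sum of daily counts over the number of valid days. Weekday counts come from a direct question about toilet use and need no volume.

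**The concern.** The two weekend rules agree only when every toilet entry on a valid weekend day carries a volume. The plan itself allows for days when that is not so. One positive volume makes the day valid, and the statement that an episode counts without a volume would have no purpose if every void were measured. SAP 5.2.1 also divides by the number of times a volume was recorded, so the SAP treats recorded volumes as a count in their own right.

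On a partly measured day the amount-recorded total omits real voids. It also makes one 7-day mean mix two definitions: all toilet visits on weekdays, and only measured voids at the weekend. If a family measures fewer voids at week 12 than at baseline, frequency appears to fall although voiding has not changed.

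The derived variable feeds the primary ANCOVA (6.4.1.1), its sensitivity analyses (6.4.1.3) and the futility calculation (6.9). The 5.2.4 variable is a secondary endpoint. An unambiguous count should be in the text before unblinding, so that no choice about it is left until afterwards.

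**Working it through.** **The plan's own figures.** SAP 3 gives an effect of 0.9, a common SD of 2.3, 80% power and 82 evaluable children per arm; 6.4.1.1 tests two-sided at 10%.

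- Normal approximation: n = 2 × (1.645 + 0.842)² × (2.3/0.9)² ≈ 80.8, so 81 per arm. The t-test solution is 81.4, so 82.
- Power at 82 per arm is 0.805 (normal) or 0.802 (t-test).
- With 10% not evaluable, 82/0.90 = 91.1, so 92 per arm and 184 in total.

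The sample size reproduces, and the counting rule does not alter it. The effect and SD serve below as yardsticks.

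**Inputs for the gap.** There are two weekend days per diary (SAP 2.2). D is the number of valid diary days, 4 to 7 (SAP 5.1). k is the number of toilet entries without a volume on each weekend day. The documents do not give k, so it is varied.

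**One visit, one child.** Let S be all toilet entries over the valid days, with both weekend days valid.

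- Toilet-entry rule: mean = S/D.
- Amount-recorded rule: mean = (S − 2k)/D.
- Gap = 2k/D. If only one weekend day is valid, the gap is k/D.

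| D | k=1 | k=2 | k=3 |
|---|---|---|---|
| 7 | 0.29 | 0.57 | 0.86 |
| 6 | 0.33 | 0.67 | 1.00 |
| 5 | 0.40 | 0.80 | 1.20 |
| 4 | 0.50 | 1.00 | 1.50 |

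If no volume is recorded on a weekend day, the day is missing under both rules and creates no gap.

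**Change from baseline.** The two rules give changes that differ by −(2k₁₂/D₁₂ − 2k₀/D₀), where the subscripts denote week 12 and baseline. If k/D is the same at both visits, the difference is zero.

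Example: a child voids 8 times every day, with 7 valid days at both visits. All voids are measured at baseline, and one per weekend day is unmeasured at week 12. The toilet-entry rule gives a change of 0. The amount-recorded rule gives (5×8 + 2×7)/7 − 8 = 7.71 − 8 = −0.29.

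**Treatment contrast.** The shift is the between-arm difference in the mean of that quantity. As an illustration only, suppose everything is measured at baseline, D=7, and the arms differ by 0.5 unmeasured voids per weekend day at week 12. The shift is 2×0.5/7 = 0.14, or 16% of 0.9.

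A constant share f of unmeasured weekend voids, rather than a constant number, is a special case, because the number unmeasured then falls as voiding falls. The effect is scaled by (5 + 2(1 − f))/7. At f=0.1 this is 0.971, which turns 0.9 into 0.874.

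**The case against.** The strongest reply is that 5.1 already settles the matter. The only sentence that speaks directly to voids without a volume says they count. It comes after the disputed sentence, and the source definition and the daytime and nighttime definitions all use toilet entries. The disputed sentence sums daytime and nighttime, the two quantities just defined, so it can be read as loose wording for their total. Most of this stands: the intended rule can be recovered. A reader might infer that the primary endpoint is left open between two equally supported rules, and the documents do not support that. What remains is a sentence that states a wrong total in 5.1, and again in 5.2.4, where the correcting statement is absent.

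A reader might also infer that one child's primary endpoint can move by about the planned effect of 0.9. The arithmetic permits it only under assumed and fairly extreme conditions. At D=7 it needs k = 0.9×7/2 = 3.15 on both weekend days at one visit and none at the other; at D=4 it needs k = 1.8. The comparison is also wrong in kind, because 0.9 is a difference between arm means. The per-child yardstick is the SD of 2.3, against which 0.29 is about 0.12 SD (0.286/2.3).

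Pure noise would cost little. If the gap in the change score had an independent SD of 0.57, the total SD would be √(2.3² + 0.57²) = 2.37, and power at 82 per arm would fall from 0.805 to about 0.784 (normal approximation). Bias in the contrast needs the shift in measuring to differ by arm. The trial is randomized and double-blind, and the documents give no reason to expect a difference in measuring effort between arms.

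**Conclusion.** The contradiction is in the current SAP text and sits in the derivation of the primary endpoint and one secondary endpoint. The amount-recorded sentence is the wrong one: it conflicts with the rest of 5.1 and undercounts on any valid weekend day with an unmeasured void.

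With both weekend days valid, the undercount in one child's visit mean is 2k/D. For one or two unmeasured voids per weekend day that is 0.29 or 0.57 with 7 valid days; for one it is 0.50 with 4 valid days. These sizes rest on assumed values of k. They carry into the change from baseline only as far as k/D differs between baseline and week 12, and into the treatment contrast only as far as that difference varies by arm. No estimate of bias in the trial result can be made from the documents. The case for correction is that the sentence is wrong, affects the primary endpoint, and costs almost nothing to replace.

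**What to change.** Before database lock, replace the amount-recorded sentence in both places:

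- **SAP 5.1:** state that the weekend-day count is the number of 'Pee in toilet' plus 'Pee in toilet and leakage' entries on a valid diary day, whether or not a volume is given.
- **SAP 5.2.4:** state the same rule for the daytime count, keeping the existing treatment of the first void at or after waking.

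Keep the rule in SAP 5 that a weekend day needs at least one positive volume to be valid, and the rule in 5.1 that a weekend day with no volume is missing. It would be tempting to add that volumes are used only for the volume endpoints. That would collide with both rules and change which weekend days enter the primary endpoint.

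The cost is one sentence in each of two sections, plus a check that the derivation program, including the one used for the futility analysis, counts toilet entries. No new data are needed, and the sample size does not change.
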